3.5.2. Exclusion and Stop Criteria

Pre-PDC Phase One:

1. Any infant whose family is unwilling to consent to study or decides to stop the home visit at any time.
2. Congenital heart disease per neonatal register
3. Genetic dysmorphology per neonatal register
4. Birth asphyxia per neonatal register

Post-PDC Phase Two:

1. For Aim 4a, exclusion criteria will match the Baseline Phase One exclusion criteria listed above.

Expanding-PDC Phase Three:

1. Children who do not meet inclusion criteria will be excluded.

3.5.3 Sampling

Pre-PDC Phase One:

Potential participants will be identified and sampling will be conducted in the following manner. The study coordinator will use the Rwinkwavu neonatal registry after obtaining consent from the medical director to identify potential study participants based on the inclusion criteria outlined above. The following identifiers will be extracted from the registry: name, sex, date of birth, discharge date and mother's name. After the identification of potential participants, the patient files will be located and examined to compile the demographic information of the infants: sector, cell, village, and health center.

Post-PDC Phase Two:

All children enrolled in the PDC are eligible and no new data will be collected for Aim 3. Children will be identified through PDC patient records, which include patient registers, patient enrollment forms, routine program forms, and the electronic medical record (EMR). To complete Aim 4, additional assessments of children's growth, development, and home environment including parenting practices will be conducted through household interviews with the primary

caregivers of PDC patients. Patient names and household location will be extracted from the EMR of patients who enrolled in the PDC at least 12 months prior to data collection.

Expanding-PDC Phase Three:

All children enrolled in the neonatal units or PDC, their caregivers, and PDC providers are eligible for participation in this aim. Children will be identified through neonatal unit and PDC patient records, which include patient registers/charts, patient enrollment forms, routine program forms, and the electronic medical record (EMR).

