3.3. Study sites

Pre-PDC Phase One:

Phase One data collection took place in the Rwinkwavu District Hospital catchment area: Nyamirama, Mukarange, Mwili, Murama, Rwinkwavu, Kabarondo, Ndego, Kabare, and Ruramira sectors.

Post-PDC Phase Two:

Phase Two data collection will take place in the PDC clinics in the Rwinkwavu District Hospital catchment area: Rwinkwavu, Kabarondo, Ndego, Cyarubare and Ruramira Health Centers. Additional data collection on patient outcomes will be collected during household interviews at the homes of PDC patients.

Expanding -PDC Phase Three:

Data collection will take place in all PDC clinics in the Rwinkwavu and Kirehe District Hospital catchment areas. Household data collection will be conducted in the communities of Kirehe District.

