3.4. Study population

Pre-PDC Phase One:

All infants discharged from the Rwinkwavu District Hospital neonatal unit during the designated time period fulfilling the inclusion criteria: children were included if they were discharged between October 2011-October 2013 (prior to PDC implementation).

Post-PDC Phase Two:

All children enrolled in the PDC are eligible. PDC serves children up to age five years with prematurity, low birth weight, birth asphyxia, other perinatal risks, and other developmental delays.

Expanding-PDC Phase Three:

All children and their caregivers enrolled in the PDC clinics in S. Kayonza and Kirehe Districts are eligible. PDC serves children up to age five years with prematurity, low birth weight, birth asphyxia, other perinatal risks such as post CNS infections_cerebral malaria and meningitis, and other developmental delays.

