3.5. Selection of study population

3.5.1. Inclusion criteria

Baseline Phase One:

All infants discharged from Rwinkwavu hospital neonatal unit and born at less than 37 weeks and infants born less than 2 kilograms during the designated study period.

Post-PDC Phase Two:

All children under five years of age enrolled in PDC in Rwinkwavu District Hospital catchment area PDC clinics, will be included in Aim 3 and Aim 4b. Aim 4a will include only preterm and/or LBW (<2000g) infants for comparison with the baseline population of similar infants.

Expanding-PDC Phase Three:

All children under five years of age and their caregivers referred to or enrolled in PDC in Rwinkwavu and Kirehe District Hospital catchment areas. In addition, newborns and their caregivers from Rwinkwavu and Kirehe District Hospital catchment areas will be included as the primary referral patient population to PDC. PDC providers will also be included in some components of the evaluation.

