The majority of phase three data comes from existing program records, both paper-based and electronic as well as pre-existing de-identified data (see Appendix B for new tools being used in the PDC; Appendix F contains all the tools previously approved by RNEC). Additional data will be collected through household data collection and qualitative methods (new tools contained in Appendix B).

The procedure is as follows for using routinely collected program data: Data will be collected from electronic medical records (EMR) and paper forms that are part of routine programmatic record keeping (See Appendices B and F for all PDC data collection forms). Demographic characteristics, anthropometric measurements, clinical, counseling assessments, nutritional and developmental outcomes information will be extracted from the PDC EMR dataset and patient files. After extraction from the original dataset, data will be transferred into STATA (Stata Corp, College station, Texas, USA) for data cleaning and further statistical analysis. Patient identifiers will be removed and unique identification numbers will be assigned to the working dataset to respect patient confidentiality.

For household data collection, the procedure is as follows: neonatal unit registers will be reviewed for patients who would have been eligible for the PDC prior to the opening of the PDC in May 2015. Eligible caregivers of patients who were discharged alive will be contacted in the community to ask if they are willing to participate in the study. If caregivers provide written informed consent, they will be interviewed by trained data collectors using Android tablets about the current health, nutritional, and developmental status of their child as well as questions on the family environment. Household data collection tools are contained in Appendix A.

For qualitative data collection with PDC providers and patient caregivers, they will be invited by study staff (not PDC providers) to participate in focus groups and/or individual interviews. Only those who provide written informed consent will participate and interviews and/or focus groups

will be conducted at Partners In Health offices or other private spaces away from the PDC clinics.

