- Proportion of children with moderate or severe acute malnutrition (weight/height Z score < 2 or weight/height z score < 3) at the last visit.
- Proportion of children with a completed and documented ASQ in the reference quarter failing one or more domains on the ASQ.
- Mean/median scores on the overall ASQ
- Mortality rate in both groups
- Percentage of patients lost to follow-up
- Opportunities for learning and stimulation in the home, measured by the Rwanda-adapted HOME Inventory and the Rwanda DHS Early Childhood Development Index
- Caregiver mental health, measured by the Hopkin's Symptom Checklist which has been validated in Rwanda and used in Rwanda to assess symptoms of depression and anxiety for over twenty years
- Caregiver-child interactions and discipline practices, using the Kinyarwanda version of the Observations of Mother-Child Interactions (OMCI) as well as the Rwanda DHS Child Discipline Module
- Socioeconomic status of the household, using wealth index from the Rwanda DHS
- Exposure to daily hardships and household stressors

Expanding-PDC Phase Three:

Aim 5: To evaluate the implementation of PDC during expansion, including patient characteristics, provider experiences, quality of care, cost-effectiveness, patient experiences, and patient outcomes. Findings from this aim will be used for continuous quality improvement of the PDC and informing scale-up.

Primary Outcome: The primary outcome is the proportion of study participants alive who are meeting developmental and growth milestones.

Secondary Outcomes:

- Cost-effectiveness of the PDC model
- Adherence to PDC care protocols by PDC providers
- Quality of care
- Enrollment rates, clinic retention, and barriers to care
- Patient and provider experiences
- Impact of training and mentorship in the PDC protocol
- Evaluation of improved exclusive breastfeeding prior to PDC referral
- Impact of PDC mHealth tool on protocol adherence and child growth
- Impact of PDC on child outcomes in Kirehe

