2. The high-risk infants who were hospitalized in the neonatal unit were not from one specific sector. The Rwinkwavu Neonatal unit serves as a referral center for the Southern Kayonza district. Each of the sectors within the district may not be environmentally identical. Specifically the availability of food, amount of rain and distance to health centers are factors that could influence the outcomes of the high-risk neonates and therefore could result in residual confounding.
3. The gestational age and birth weight are subject to misclassification.
4. This is cross sectional data, and therefore any associations found are unable to assess causality.
5. Exclusion criteria undiagnosed by register are subject to misclassification.

Post-PDC Phase Two:

1. This study will be a cross-sectional study, and therefore associations may be found, but we will be unable to assess causality.
2. For the Aim 4b comparing PDC participants and UNICEF sample, only similar age groups will be compared; therefore, the number of children may be reduced which might affect the power of the study and its external validity.
3. As this is a secondary dataset analysis, missing values are expected.
4. The gestational age and adjusted age are subject to misclassification due to recall bias.

Expanding-PDC Phase Three:

1. As this is primarily a secondary dataset analysis of routinely collected data, missing values are expected.

5. Ethical Considerations

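### Aim 4a sets a baseline drawn from the neonatal register against children drawn from PDC enrolment records, so the kind of child who would not enrol is on one side only, with a bias of unknown size and direction

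*Combined protocol and SAP*

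**What the plan says.** **Baseline.** Section 3.4 takes "All infants discharged from the Rwinkwavu District Hospital neonatal unit during the designated time period fulfilling the inclusion criteria", for discharges from October 2011 to October 2013. Section 3.5.1 sets the birth criteria: "All infants discharged from Rwinkwavu hospital neonatal unit and born at less than 37 weeks and infants born less than 2 kilograms". Section 3.5.3 names the source: "The study coordinator will use the Rwinkwavu neonatal registry after obtaining consent from the medical director to identify potential study participants". Families were then reached through community health workers and asked for consent (sections 3.5.6 and 3.5.7).

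**PDC group.** Section 3.5.3 states: "Patient names and household location will be extracted from the EMR of patients who enrolled in the PDC at least 12 months prior", counted from data collection. Section 3.5.7 and the Phase Two text of section 3.6.1 use the same enrolment condition. Section 3.5.6 is stricter and asks for children seen in the clinic over 12 months or longer. Section 3.6.1 adds that PDC staff first ask caregivers whether the study team may contact them.

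**What is aligned.** For Aim 4a, section 3.5.1 restricts PDC children to preterm birth or birth weight under 2000 g, and section 3.5.2 applies the baseline exclusions. Neither section aligns the source of the children.

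**Analysis.** Section 3.6.4 compares the groups with chi-square or Fisher tests. Logistic regression follows only if power allows, and it looks for predictors of delay. Section 3.6.2 also lists mortality in both groups. The Phase Two limitations in section 4 say that causality cannot be assessed; they do not mention selection into PDC.

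**The concern.** The baseline has no uptake step. The PDC group has passed at least one: referral, reaching a clinic and enrolling, and by the section 3.5.6 wording a year of attendance as well. Matching birth criteria and exclusions does not undo that.

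The protocol itself gives grounds to expect incomplete uptake. "Enrollment rates, clinic retention, and barriers to care" are secondary outcomes, though only for Phase Three. The Phase One limitations in section 4 say that "availability of food, amount of rain and distance to health centers are factors that could influence the outcomes of the high-risk neonates". If factors of that kind also affect who enrols, the two groups differ before PDC has done anything.

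At stake is how an Aim 4a difference is read. It could reflect PDC, or who came to PDC, and without the enrolled share a reader cannot tell how much room there is for the second explanation.

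**Working it through.** **No figure to reproduce.** The protocol gives no sample size, expected rate of delay, effect size or enrolled share for Aim 4a. The check is a comparison of the two sources, followed by an illustration of size.

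**Sources side by side.**

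| | Baseline | PDC group |
|---|---|---|
| List used | Neonatal register | PDC electronic record |
| Contact condition | None | Enrolled at least 12 months earlier (3.5.3), or seen for 12 months or more (3.5.6) |
| Routes in | Neonatal-unit discharge | Neonatal unit, other hospital departments, health centres, community (3.5.5) |
| Later losses | Tracing, consent | Approach by PDC staff, tracing, consent |

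No Phase Two text traces eligible PDC-era discharges who did not enrol or who left early.

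**Size for developmental delay, assuming PDC has no effect.** Let *s* be the share of eligible discharges that enrol (and stay, where that is required), *p* the rate of delay in that type of child, and *g* the excess rate in the type that would not enrol. Assume the same mix of types in both eras.

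- PDC group rate: *p*
- Baseline rate: *s p* + (1 - *s*)(*p* + *g*) = *p* + (1 - *s*) *g*
- Spurious difference: (1 - *s*) *g*

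| Assumed *s* | Assumed *g* (points) | Spurious difference (points) |
|---|---|---|
| 0.9 | +10 | 0.1 x 10 = 1.0 |
| 0.7 | +15 | 0.3 x 15 = 4.5 |
| 0.6 | +20 | 0.4 x 20 = 8.0 |
| any | 0 | 0 |
| 0.7 | -10 | 0.3 x (-10) = -3.0 (against PDC) |

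**Chance of a significant result with no PDC effect.** This uses the two-proportion normal approximation with pooled standard error under the null. The two-sided 5% level is inferred from the 95% intervals in section 3.6.4. Rates and group sizes are assumptions.

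| *p* | *s* | *g* | Difference (points) | n = 120 per group | n = 200 | n = 400 |
|---|---|---|---|---|---|---|
| 0.30 | 0.9 | +0.1 | 1.0 | 5.3% | 5.5% | 6.1% |
| 0.30 | 0.8 | +0.2 | 4.0 | 10.2% | 13.7% | 22.8% |
| 0.30 | 0.7 | +0.2 | 6.0 | 16.7% | 24.7% | 43.8% |
| 0.50 | 0.7 | +0.2 | 6.0 | 15.3% | 22.5% | 39.7% |
| 0.30 | 0.7 | -0.1 | -3.0 | 8.1% | 10.2% | 15.6% |

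A larger sample makes this worse, because the bias stays while the standard error shrinks.

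**Mortality.** A baseline child can be counted as dead from any time after discharge. A PDC child must live to enrolment, and by the section 3.5.6 wording must live and attend for 12 months. Deaths in that interval can appear only on the baseline side.

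**The case against.** The strongest reply is that Aim 4 sets out to describe patients enrolled in PDC, and that section 4 already disclaims causality for Phase Two. That stands as far as it goes. But a general caveat does not name this selection, and it does not supply the enrolled share that a reader needs to judge it.

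Four stronger readings are tempting, and the protocol does not support them.

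- **That the bias favours PDC.** This needs non-enrolees to do worse. Distance and poverty make that plausible, but no figure shows it. Section 3.5.5 has social workers identifying financial and nutritional needs, and section 5.2 mentions food packages, which could draw poorer families in. Entry of children who already have delay is a separate problem that pushes the other way.
- **That the baseline holds every eligible child, including those PDC failed to reach.** Baseline children were discharged before PDC opened in April 2014. Only the same kind of child is there. Aim 1 calls the baseline a selected sample, and tracing and consent could lose remote families from it too.
- **That the Kirehe comparison has the same flaw.** Its pre-PDC list is indeed register-based ("neonatal unit registers will be reviewed for patients who would have been eligible for the PDC"). But the Phase Three text of sections 3.5.1, 3.5.3 and 3.5.6 covers referred children, newborns and neonatal-unit patients, and nowhere limits the later group to enrolees.
- **That clinic location gives a figure.** The baseline sectors are "Nyamirama, Mukarange, Mwili, Murama, Rwinkwavu, Kabarondo, Ndego, Kabare, and Ruramira sectors". Four of the five Phase Two clinics share a name with one of these, and the sector of the fifth is not stated, so at least four of the nine host no listed clinic. But 4/9 = 44% is a share of sector names, not of children. Taking it as one, with every child in the other sectors enrolling and outcomes 10 points worse in the four, 70% uptake gives at most (0.444 - (0.70 - 0.556)/0.70) x 10 = 2.4 points, and 90% gives (0.444 - (0.90 - 0.556)/0.90) x 10 = 0.6. Nor does lacking a clinic mean being far from one.

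**Conclusion.** The mismatch of sources in Aim 4a is in the text, and nothing in the planned analysis removes it. For developmental delay its size and direction are unknown: 1 to 8 points in favour of PDC if uptake is 60-90% and non-enrolees have 10-20 points more delay, zero if the two types do not differ, and against PDC if non-enrolees do better. All of these inputs are assumptions. For mortality, the requirement to survive to enrolment can by itself only lower the PDC figure, although other selection may offset it. The point is confined to Aim 4a. It does not show that PDC has no effect; it shows that the planned comparison cannot separate an effect from selection. The correction is cheap enough that it should be made.

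**What to change.** For Aim 4a only:

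1. Restrict PDC children to those discharged from the Rwinkwavu neonatal unit. Reconcile sections 3.5.3 and 3.5.6 on whether the condition is time since enrolment or time in attendance.
2. From the same register, list all discharges since April 2014 that meet the Aim 4a criteria, and report the share enrolled.
3. Compare enrolled with non-enrolled children on birth weight, gestational age and sex, and on sector where files allow.
4. Add an analysis that weights enrolees by the inverse probability of enrolment, so that they represent all eligible discharges.
5. Label the unweighted result 'among families who enrolled', and add selection into PDC to the Phase Two limitations as a bias of unknown direction.
6. Do not read the mortality difference as a PDC effect unless deaths are ascertained for all register-eligible children, or both groups are restricted to survivors to a common age.

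**Cost.** No extra home visits for steps 1 to 5; ascertaining deaths among non-enrolees would need tracing, and the survivor restriction in step 6 avoids that. Section 3.5.3 takes sector from individual patient files rather than the register, so step 3 involves file review, and step 2 needs linkage by name to the electronic record. Intervals will be slightly wider. Weighting on these variables does not remove differences in motivation or wealth, and it cannot restore deaths before enrolment.

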3.5.4. Randomization

None

3.5.5. Proposed Intervention

Children in Phases Two and Three of this study have participated in the PDC program as described previously, unless they are in a comparison group. The PDC provides medical, nutritional and developmental supportive programs to at-risk children under age five using trained nurses and social workers in addition to overall clinic supervision by a general practitioner. Children are referred to the PDC from the hospital (neonatal unit, maternity, inpatient pediatrics, and the outpatient or emergency departments), health centers, and from the community. Children are eligible to enroll in the PDC if they meet the following program eligibility criteria: prematurity, low birth weight (<2000grams), hypoxic ischemic encephalopathy, hydrocephalus, cleft lip and palate, trisomy 21, post central nervous system infections (meningitis and cerebral malaria) severely malnourished children requiring hospitalization post-discharge, as well as children presenting with other developmental delays. Children come in for routine visits, on a timeline determined by their specific condition. On each PDC clinic day, social workers facilitate a group counseling session focused on topics relevant to children's growth and development. After group sessions, children undergo a clinical screening and growth monitoring by a nurse as well as one-on-one sessions with a social worker to identify needs for additional social support whether financial, emotional, nutritional, or a home visit. PDC social support groups are formed to engage father's in the care of their children. Health

center PDC clinics receive mentorship visits from the hospital PDC supervision team; mentors use structured observation checklists for monitoring quality of care delivery and data-feedback. An application to aid decision making using tablets has been designed to address challenges with growth monitoring especially for preterm infants and identification of feeding difficulties, which has limited the PDC's ability to successfully provide early intervention in cases of growth failure. The mHealth tool supports providers in calculating z-scores, interval growth, and adjusted age as well as providing counseling that is tailored to the individual child's needs. Also, in an effort to optimize nutritional outcomes of babies discharged from Rwinkwavu and Kirehe Neonatal Units, as part of phase 3 of the project, we will also be implementing interventions to promote breastfeeding from as early as day one of life. This will primarily be done through early, individualized counseling and education on the importance and best techniques for breastfeeding and expressing breast milk, but will also employ visual aids such as posters and videos, and the institution of a policy to restrict use of artificial milk to clinically indicated situations, such as growth failure that requires breast milk supplementation to provide additional calories, or within the first two weeks of life if the mother has insufficient breast milk production, to avoid negative effects on growth. By targeting mothers and infants in the Neonatal Unit to establish strong breastfeeding during admission, growth of high-risk infants will be optimized from day one of life, and babies will also experience additional benefits of breast milk such as reduced infections and improved neurodevelopmental outcomes before they are discharged for follow-up in PDC. Future, planned interventions are to promote maternal nutrition by providing supplementary meals and involving our maternity department in counseling mothers on early initiation of breastfeeding for all babies, and expressing breast milk for babies who are unable to breastfeed due to prematurity or their clinical status.

[**3.5.6. Recruitment Methods**](#)

Pre-PDC Phase One:

Our data collection is based on the use of independent data collectors. Data collection officers will be identified from the Family Strengthening Intervention Study staff (through coordination with their study coordinator) and will be trained on the use of the Ages and Stages Questionnaire as well as weight, length and head circumference measurements. Training sessions will take place at Rwinkwavu Center for Training and Operational Research. After completion of training, the data collection officers will be given a list of potential study participants. The data officers

will then contact the family's community health worker prior to making home visits and approaching the family for study participation.

Post-PDC Phase Two: All children enrolled in the PDC are eligible and the study will use routinely collected data from patient charts and EMR. In addition, patients who have been seen in the PDC clinic for 12 or more months will be contacted to participate in a household interview to be conducted by trained, independent data collectors. Patients will be identified from PDC enrollment records, and information will be extracted from patient charts for follow-up in the community (this includes caregiver name, geographic location of the household, and any relevant contact information for the household such as a phone number). Data officers will then contact the family's community health worker prior to making home visits and approaching the family for study participation.

Expanding-PDC Phase Three:

All children enrolled in the hospital neonatal units or PDC, and their caregivers, are eligible. The study will use routinely collected data from patient registers, patient charts and EMR in addition to qualitative methods. In addition, a list of PDC-eligible children prior to the opening of PDC in Kirehe (i.e., before May 2016) will be identified for household data collection to establish baseline status of high-risk infants prior to PDC. PDC providers (nurses, doctors, social workers, other parahealth professionals, volunteers) will be eligible to participate if they have been working in the PDC for at least 3 months.

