Patient flow: Group education, individual social worker screening, clinical evaluation including danger sign assessment, nutritional assessment/classification/treatment, developmental screening/therapy, and condition-specific screening and treatment.

Aim 4: Compare developmental, medical, and nutritional outcomes of children who were enrolled in the PDC to other children on the main outcomes of prevalence of developmental delay as measured using the Ages and Stages Questionnaires (ASQ-3) and the prevalence of undernutrition (stunting, wasting, underweight) using anthropometric assessments.

This aim is to describe the clinical, nutritional, and developmental outcomes of vulnerable patients enrolled in PDC in comparison with:

- a. Medically vulnerable infants who did not receive PDC support. This comparison will be made using a cohort of preterm/LBW children who were born in Rwinkwavu District Hospital (RDH) before PDC started with medical, nutritional and developmental outcomes assessed at 12-36 months of age (the dataset from Aim 1).
- b. The general population of rural Rwandan children.² This comparison will be looking at developmental outcomes of children followed in PDC compared to the similar age children from the general population using UNICEF data that was collected in children ages 0-11 months and 24-35 months randomly sampled from ten rural sectors of the country.

Additional variables to be measured include (See Appendix F for data source forms of routinely collected data and Appendix A for household interview forms. All measures used in the household interview were previously used in the two comparison datasets):

- Descriptive characteristics of caregivers.
- Proportion of visits where a nutritional screening was done, danger sign screening was done, and patient had a documented ASQ within the 6 months prior to visit date.

² This existing data set was collected by UNICEF, Harvard School of Public Health, Partners In Health, and the University of Rwanda. [name] and [name] were investigators on both study teams and have access to the data.

- Proportion of children who received nutrition supplement.
- Proportion of currently enrolled children with a visit in the reference quarter whose caregivers have had at least one documented ECD counseling session
- Proportion of children with moderate or severe chronic malnutrition (height/age Z score < 2 or height/age z score < 3) at the last visit.

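### Aim 4a draws its two arms from different frames: the comparator is neonatal-unit discharges, while the PDC arm is preterm/LBW enrollees by any route, some possibly referred because of the outcome

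*Combined protocol and SAP*

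**What the plan says.** **Comparator.** Section 3.5.1 defines Phase One as "All infants discharged from Rwinkwavu hospital neonatal unit and born at less than 37 weeks and infants born less than 2 kilograms". Section 3.5.3 gives the sampling frame: "The study coordinator will use the Rwinkwavu neonatal registry". Section 3.4 limits it to discharges from October 2011 to October 2013, before the PDC opened. Section 3.6.2 describes the same group differently, as a "cohort of preterm/LBW children who were born in Rwinkwavu District Hospital (RDH) before PDC started", without mentioning the neonatal unit.

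**PDC arm.** Section 3.5.1 states: "Aim 4a will include only preterm and/or LBW (<2000g) infants for comparison with the baseline population of similar infants". Section 3.5.3 identifies children for the Aim 4 household interviews from the electronic medical record (EMR), provided they enrolled at least 12 months before data collection. On entry to the programme, Section 3.5.5 says "Children are referred to the PDC from the hospital (neonatal unit, maternity, inpatient pediatrics, and the outpatient or emergency departments), health centers", and adds the community. Its eligibility list includes prematurity and birth weight below 2000 g, and also severe malnutrition requiring hospitalization and other developmental delays.

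**Exclusions.** Section 3.5.2 states: "For Aim 4a, exclusion criteria will match the Baseline Phase One exclusion criteria listed above". Of the four Phase One criteria, three (congenital heart disease, genetic dysmorphology, birth asphyxia) are taken from the neonatal register. The fourth is refusal or stopping of the visit.

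**Analysis.** Section 3.6.4 plans an unadjusted chi-square or Fisher test. Logistic regression on predictors of delay follows only if power allows, and referral source is not named as a covariate. The main outcomes in Section 3.6.2 are developmental delay on the ASQ-3 and undernutrition.

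**The concern.** A Phase One child enters because of how it was born and where it was discharged from, whatever happened later. A PDC child must be preterm or low birth weight, but nothing requires that it was discharged from the neonatal unit, was referred from there, or enrolled before a problem appeared. A preterm child sent at a later age from inpatient pediatrics, a health center or the community because of malnutrition or delay passes the Aim 4a filter. Selection into that arm can then depend on the outcome being compared, and an unadjusted test cannot separate this from an effect of the PDC.

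The exclusions add a second asymmetry. The plan does not say how a register-based diagnosis is to be established for a PDC child who was never in the unit. If PDC records are used instead, the two arms are screened by different sources.

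Aim 4a is the plan's comparison with similar high-risk children who had no PDC, so a frame mismatch could hide a real benefit or create an apparent one.

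**Working it through.** **Step 1: the frames side by side.**

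| | Phase One comparator | Aim 4a PDC arm |
|---|---|---|
| Source | Neonatal register | PDC EMR |
| Birth criterion | <37 weeks, or <2 kg | Preterm and/or <2000 g |
| Neonatal-unit discharge required | Yes | Not stated |
| Referral route or reason | Not applicable | Not restricted |
| Time in programme | Not applicable | At least 12 months |
| Three clinical exclusions | From the register | Same list; source undefined for children not in the register |

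The birth-weight and prematurity filter removes children eligible only through delay or malnutrition. It does not remove preterm/LBW children who arrived because of delay or malnutrition.

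**Step 2: is there a plan figure to reproduce?** No. The documents state no sample size, power, delay rate or split by referral route for Aim 4a. The only count is 120 incentive units in the Phase One budget (Section 6.3). That is not a sample size, and its line does not multiply out (150 × 120 = 18,000, shown as 180,000). Below, n = 120 per arm and a two-sided 5% level are assumptions.

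**Step 3: illustration with no true PDC effect.** Let f be the share of the PDC arm referred because of delay, q their delay rate at assessment, and p the rate in everyone else, including the comparator.

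- PDC-arm rate = (1 − f)p + fq, so the shift is f(q − p).
- With p = 40% and q = 80%, f = 10%, 20%, 30% gives shifts of 0.1 × 40 = 4, 0.2 × 40 = 8 and 0.3 × 40 = 12 points.
- Chance of a significant result against the PDC = Φ[(d − 1.96·SE0)/SE1], where d is the shift, SE0 = √(2·p̄(1 − p̄)/n) with p̄ the mean of the two rates, and SE1 = √(p0(1 − p0)/n + p1(1 − p1)/n).
- For f = 20%: p1 = 0.48, SE0 = √(2 × 0.44 × 0.56/120) = 0.0641, SE1 = √((0.24 + 0.2496)/120) = 0.0639. This gives Φ[(0.08 − 0.1256)/0.0639] = 0.238.

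Without bias this chance is about 0.025. Each cell gives the shift in points, then the chance. Ranges are for q = 80% to 95%; the 40% row uses q = 80% only.

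| Comparator rate | f = 10% | f = 20% | f = 30% |
|---|---|---|---|
| 30% | 5.0-6.5; 0.128-0.186 | 10-13; 0.368-0.553 | 15-19.5; 0.672-0.875 |
| 40% | 4; 0.091 | 8; 0.238 | 12; 0.462 |
| 50% | 3.0-4.5; 0.067-0.103 | 6-9; 0.151-0.287 | 9-13.5; 0.287-0.560 |
| 70% | 1.0-2.5; 0.037-0.063 | 2-5; 0.053-0.137 | 3-7.5; 0.074-0.260 |

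**Step 4: illustration with a true 15-point reduction.** Assume 40% falls to 25% in children not referred for the outcome, and outcome-referred children stay at 80%. The PDC-arm rate is 0.25(1 − f) + 0.80f, which is 25%, 30.5%, 36% and 41.5% for f = 0, 10%, 20% and 30%. The chance of showing the benefit falls from 0.70 to 0.34, 0.09 and 0.01. At a 70% comparator rate the same 15-point effect has power 0.67 with f = 0, 0.52 with f = 10% and 0.37 with f = 20%.

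**Step 5: forces in the other direction.** If a share g of the PDC arm never needed the neonatal unit (for example, referred from maternity) and has a lower delay rate r, the PDC-arm rate moves by −g(p − r). Requiring at least 12 months of enrolment may also select families and children who do better. The documents give no value for g, r or retention, so the sum of these terms has no known sign.

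**The case against.** The strongest reply is that the mismatch may be small. Section 3.5.5 lists routes and entry grounds for the whole programme, including trisomy 21 and cleft palate. It does not say that preterm/LBW children come by every route. Such children qualify at birth without any later problem, and most could have been referred straight from the neonatal unit. Section 3.5.1 (Phase Three) calls newborns the main referral population. Without a route split, the outcome-referred share could be close to zero. This stands as to size. It does not close the gap, because the plan neither ensures nor checks it.

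A reader might infer that delayed or malnourished children appear in the PDC arm only. The documents do not support that: Phase One contains them at their natural frequency. What can occur in one arm only is selection because of those conditions. Nor are all four exclusions register-based; three are.

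It is also fair to say that Aim 4 is descriptive and that the Phase Two limitations in Section 4 already disclaim causality. But that disclaimer rests on the cross-sectional design and does not mention different frames. The remark on exclusions undiagnosed by the register appears only under Phase One.

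**Conclusion.** The point holds: the Aim 4a arms have different sampling frames, PDC entry can depend on the outcome, and three exclusions cannot be applied alike in both arms. No passage repairs this, and the planned test does not adjust for it.

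A reader might go further and conclude that Aim 4a is biased against the PDC by a known amount. The documents do not support that. Outcome-triggered referral alone works against the PDC, but healthier maternity referrals and the 12-month rule may work towards it, so the net direction is uncertain. Every figure above rests on assumed f, q, p and n. The shift of 4 to 12 points is one scenario; at a 70% comparator rate with f = 10-20% it is 1 to 5 points. If nearly all preterm/LBW PDC children were referred at neonatal-unit discharge, this source of bias is minor. I rate it a cheap improvement rather than a flaw of demonstrated size.

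**What to change.** 1. In Section 3.5.1, define the primary Aim 4a PDC arm as children found in the Rwinkwavu neonatal register as discharged alive and referred to the PDC at that discharge. Neonatal-unit discharge alone is not enough, because a unit graduate who enrols later because of delay would still be selected on the outcome.
2. In Section 3.5.2, state that the three register-based exclusions are taken from the register in both arms.
3. Extract referral source, reason for referral and age at enrolment for each child from PDC records. Aim 3 describes the referral system, but its variable list in Section 3.6.2 shows no child-level referral source, so availability should be checked first.
4. Report children from other routes descriptively, and run an all-routes sensitivity analysis.
5. Add the remaining selection by uptake and 12-month retention to the Phase Two limitations. The restriction does not remove it, since the comparator is all eligible discharges and the PDC arm is only those who enrolled and reached 12 months.
6. Reconcile the two descriptions of the comparator: born in the district hospital, or discharged from its neonatal unit.

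The cost is a smaller PDC arm, by an amount the documents do not allow one to estimate, and a cross-check of PDC records against the register. The register is not among the Phase Two data sources, so it needs adding. Section 3.5.3 shows that name, sex, date of birth, discharge date and mother's name were extracted from it for Phase One, which gives fields for matching. The arm definition should be fixed before the outcomes are compared.
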